15.1.3 Primary Analysis of Primary Variable

The primary objective of this study is to demonstrate if discontinuation of nocturnal use of absorbent pants in children with NE has any impact on the rate of spontaneous resolution of NE, compared with continued use of absorbent pants, over a period of 4 weeks.

The primary effectiveness analysis will be performed for the PAS comparing the 95% CI for the difference between the means of average wet nights at the end of intervention period for the 2 groups with the predefined margin ($\delta = 2/7$). If the CI lies strictly within [- δ , + δ], the study hypothesis will be demonstrated. Difference in means and CI will be generated by PROC TTEST for independent groups.

Primary analysis will be also repeated by age groups (4–<6 years and \geq 6–8 years).

Document:	Y:\Kimberly-Clark\DryNites\Documentation\SAP\DryNites_SAP_v1.0_20200203		
Author:	[name]	Version Number:	1.0
		Version Date:	03Feb2020
Template No.: F	RWI_TP_BIOS0013 Revision 1		Reference: RWI_WI_BIOS0015
Effective Date:	15Jun2018		

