#### Sample size

The statistical hypothesis behind the present study design is the equivalence in rate of spontaneous resolution of NE at  $56 \pm 7$  days between discontinuing and continuing nocturnal use of DryNites® absorbent pyjama pants in children with NE. The margin for non-inferiority is set to 2/7 wet nights with an expected proportion of 0.95 and 0.80 wet nights, respectively for continuing and discontinuing use of absorbent pants group. The power is set to 99%.

Fifteen participants are needed in the continuation arm to obtain a power of 99%. This means that a total of 45 participants are needed at randomisation (due to the 2:1 randomisation). Fifteen additional participants are added to this number (total of 60 participants) to compensate for dropouts/poor compliance during the trial, and for the participants who will be excluded at randomisation because they did not fulfil the criteria of 7 wet nights per week. Additionally, the primary endpoint will be analysed separately for the 2 age groups (4–<6 and  $\geq$ 6–8 years of age) and therefore 60 participants will be needed for each age group (total 120 participants).

As such, 120 participants should be recruited, with approximately half of the participants should be in the younger age group, age 4-<6 years, and half of the participants should be in the older age group,  $\ge 6-8$  years.

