#### 5 STATISTICAL METHODS

#### 5.1. Statistical Hypotheses

The statistical hypothesis behind the present study design is the equivalence in rate of spontaneous resolution of NE at  $56 \pm 7$  days between discontinuing and continuing nocturnal use of DryNites® absorbent pyjama pants in children with NE. The margin is set to 2/7 wet nights with an expected proportion of 0.95 and 0.80 wet nights, respectively for continuing and discontinuing use of absorbent pants group. The power is set to 99%.

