The primary outcome (i.e., average number of wet nights in Week 4 of the core study period) will be analysed for the Primary Analysis Set comparing the 95% CI for the difference between the means of the 2 groups with the predefined margin ( $\delta = 2/7$ ). If the CI lies strictly within [- $\delta$ , + $\delta$ ], the study hypothesis will be demonstrated.

QoL and sleep quality endpoints will be assessed analysing the following questionnaires:

- Paediatric Incontinence Questionnaire
- World Health Organization Quality of Life
- Paediatric Daytime Sleepiness Scale
- Checklist Individual Strength

The PinQ measures the emotional impact that urinary incontinence has on a child. It consists of 20 urinary incontinence QoL related questions which are graded on a scale of 0–4 (0=No, 1=Hardly ever, 2=Sometimes, 3=Often, 4=All the time) with a total possible score of 80.

The total score indicates the impact urinary incontinence has on the child's QoL with the higher score indicating a more significant effect.

The WHOQoL-BREF assesses the individual's perceptions in the context of their culture and value systems, and their personal goals, standards, and concerns. It comprises 26 items, which measure the following broad domains: physical health, psychological health, social relationships, and environment. Domain scores are scaled in a positive direction (i.e., higher scores denote higher QoL). The mean score of items within each domain is used to calculate the domain score. Mean scores are then multiplied by 4 in order to make domain scores comparable with the scores used in the WHOQoL-100 (WHO 1996).

The PDSS questionnaire has been developed to measure daytime sleepiness of middle-school children and examine the relationship between daytime sleepiness and school-related outcomes. It consists of 8 items (0–4-point scale) with higher scores associated with reduced total sleep time, poorer school achievement, poorer anger control, and frequent illness. The total score will be calculated as sum of each item response.

The CIS is a 20-item fatigue questionnaire for which the person indicates on a 7-point scale to what extent a particular statement applies to him or her and it measures 4 dimensions of fatigue: fatigue severity (items 1, 4, 6, 9, 12, 14, 16, 20), concentration problems (3, 8, 11, 13, 19), reduced motivation (2, 5, 15, 18) and activity (7, 10, 17). The CIS total score can be calculated by adding the 4 dimensions.

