8. STATISTICAL CONSIDERATIONS

8.1 Statistical Tests and Confidence Intervals

Unless otherwise specified in the description of the analyses, a two-sided 95% CI will be considered as a default (alpha= 5%). The equivalence margin is set to 2/7 wet nights with an expected proportion of 0.95 and 0.80 wet nights, respectively for continuing and discontinuing use of absorbent pants group.

No confirmatory testing is planned, p-values are provided as descriptive representations of the data.

Document:	Y:\Kimberly-Clark\DryNites\Documentation\SAP\DryNites_SAP_v1.0_20200203			
Author:	[name] Version Number:		1.0	
		Version Date:		03Feb2020
Template No.: RWI_TP_BIOS0013 Revision 1			Reference:	RWI_WI_BIOS0015
Effective Date: 15Jun2018				

Statistical Analysis Plan

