15.1 Primary Analysis

The primary analysis will be performed separately for age groups for the PAS comparing the 95% CI for the difference between the means of average wet nights at the end of intervention period for the 2 groups with the predefined margin. Being the primary analysis focused on last week of the intervention period (lasting from randomisation to Visit 3) and the equivalence margin reported as 2/7 (two nights over a week), the average number of wet nights was chosen as reliable outcome on primary endpoint.

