15.1.1 Primary Analysis Variable & Derivation

The primary analysis variable will be the difference between the 2 groups on the average number of wet nights in Week 4 of the intervention study period and will be derived using the item "Did the child have an NE (nocturnal enuresis) event?" collected on daily diary. The number of "Yes" for each patient will be counted over the last 7 days of the intervention period (from randomisation till the Visit 3 day).

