15.1.2 Missing Data Methods for Primary Analysis Variable

Multiple imputation technique will be used to address missing values for primary endpoint in case of percentage of missing data will be $\geq 20\%$. Multiple imputation it's superior to single imputation in reducing statistical bias by building in random error into the imputation. This prevents underestimation of the degree of variability in the data, which affects the estimate of the standard error.

Document:	Y:\Kimberly-Clark\DryNites\Documentation\SAP\DryNites_SAP_v1.0_20200203		
Author:	[name]	Version Number:	1.0
		Version Date:	03Feb2020
Template No.:	RWI_TP_BIOS0013 Revision 1	I	Reference: RWI_WI_BIOS0015
Effective Date:	15Jun2018		

The following steps will be used:

- Differences on all key and outcome variables between patients with missing versus nonmissing values will be described and tabulated.
- Missing data will be imputed using SAS PROC MI under the assumption that the missing values are missing at random (MAR). This assumption requires that missing values be related to measured covariates, with no unmeasured related covariates.
- Results will be aggregated across the multiply imputed data sets using SAS PROC MIANALYZE.

The multiple imputation model will include the primary outcome as the number of wet nights during the last week on the 4 weeks period after randomisation, randomisation group, average number of wet nights during the run-in period, age and sex. The number of imputation data sets to be created is 100.

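### The primary rule compares a 0–7 count of wet nights with a margin of 2/7 that was set on the proportion scale; read literally, equivalence cannot be shown at the planned rates

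*SAP*

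**What the plan says.** **Margin.** Protocol 5.2 works on the risk difference between two nightly probabilities, 0.95 (continue) and 0.80 (stop), and says that δ = 2/7 corresponds to 2 nights per week. Protocol 5.4.6 also gives the margin as 2 nights per week, based on feedback from families. SAP 15.1 agrees: "the equivalence margin reported as 2/7 (two nights over a week"). Protocol 4.5.1 treats a reduction of at least 2.0 wet nights per week as clinically significant. Elsewhere the unit slips. Protocol 5.1 says "The margin is set to 2/7 wet nights with an expected proportion of 0.95 and 0.80 wet nights", and SAP 4.1, SAP 8.1 and the synopsis carry nearly the same phrase.

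**Outcome.** SAP 15.1.1 takes the affirmative diary answers, which "for each patient will be counted over the last 7 days of the intervention period (from randomisation till the Visit 3 day"). That is a whole number from 0 to 7. SAP 15.1.2 enters into the imputation model "the primary outcome as the number of wet nights during the last week on the 4 weeks period after randomisation".

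**Decision rule.** SAP 15.1.3 rests on "comparing the 95% CI for the difference between the means of average wet nights at the end of intervention period for the 2 groups". It obtains the difference in means and its 95% CI from PROC TTEST and requires the CI to lie inside ±2/7. Protocol 5.4.2 has the same rule, "comparing the 95% CI for the difference between the means of the 2 groups with the predefined margin", without naming a procedure.

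**The concern.** The margin belongs to a quantity between 0 and 1, and the outcome as derived runs from 0 to 7. A programmer who follows SAP 15.1.1 and 15.1.3 line by line would test a margin of 0.286 nights per week, one seventh of the intended margin. This rule alone decides whether the study hypothesis is declared demonstrated. If the plan's own assumption is true, the two readings give opposite primary conclusions from the same data. The trial is open-label, so settling the scale after results are visible would look like choosing the scale by its outcome.

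**Working it through.** **Inputs.** Wet nights per child are Binomial(7, p), with p = 0.95 (continue) and 0.80 (stop), nights independent, and a two-sided 95% CI (Protocol 5.2; SAP 8.1). Allocation is 1:2. Sizes, continue/stop:
- 15/30: evaluable number per age group (Protocol 5.2).
- 20/40: 60 per age group split 1:2.
- 30/60: evaluable number for both age groups together.
- 40/80: the 120 that Protocol 4.3 aims to randomise, split 1:2. This is a ceiling, because Protocol 5.2 counts dropouts and run-in failures within the 120.

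**Step 1: the plan's own figure.** Protocol 5.2 states 99% power at 15/30 on the proportion scale. Simulation gives 97.7% with a Wald interval on nights and 97.8% with a Newcombe interval, within 2 points of the stated value. So the sample size was worked out with outcome and margin both on the proportion scale.

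**Step 2: planned difference against the literal margin.** The difference is 7 × (0.95 − 0.80) = 1.05 nights. The literal margin is 2/7 = 0.286, and 1.05 / 0.286 = 3.7. Because the assumed true difference lies outside the literal margin, a larger sample cannot help.

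**Step 3: width of the interval.** The variance per child is 7 × 0.95 × 0.05 = 0.3325 (continue) and 7 × 0.80 × 0.20 = 1.12 (stop).
- 15/30: SE = √(0.3325/15 + 1.12/30) = 0.244; half-width 1.96 × 0.244 = 0.478 nights.
- 40/80: SE = √(0.3325/40 + 1.12/80) = 0.149; half-width 0.293 nights.

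The expected CI at 40/80 is 1.05 ± 0.293, or 0.76 to 1.34 nights. It lies wholly outside ±0.286 and well inside ±2. Divided by 7 it is 0.108 to 0.192, inside ±2/7.

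**Step 4: chance that the literal rule succeeds at 0.95 vs 0.80.** The normal approximation is Φ((0.286 − 1.05)/SE − 1.96), which gives 1.8 × 10⁻⁷ at 15/30 and 7 × 10⁻¹³ at 40/80.

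**Step 5: simulation with t intervals** (40,000 trials per setting). SAP 15.1.3 does not say whether the pooled or the Satterthwaite interval applies, so where two figures are given they are pooled / Satterthwaite.

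| Continue/stop | Literal, 0.95 vs 0.80 | Literal, both arms 0.95 (assumed) | Matched scales, 0.95 vs 0.80 |
|---|---|---|---|
| 15/30 | 0% | about 1% | 91% / 97% |
| 20/40 | 0% | about 4% | 98% / 99% |
| 30/60 | 0% | about 20% | 99.9% / 100% |
| 40/80 | 0% | about 44% | 100% / 100% |

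Count against 2.0 and count/7 against 2/7 are the same test, so the last column serves for both repairs.

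**Step 6: sensitivity to assumptions that the documents do not give.** At 40/80 with equal arms, the literal rule succeeds in about 2% of trials at 0.90, 79% at 0.97 and over 99% at 0.99. At equal 0.95 with a within-child correlation of 0.3, the 44% falls to about 3%.

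**The case against.** The strongest reply is that the text already points to proportions. The sentence that gives the margin also gives the rates as proportions, and 0.95 or 0.80 of a wet night per week would make no sense for children randomised on 7 wet nights out of 7. SAP 15.1 and 15.1.3 speak of means of an average, which is natural if each child's value is a nightly average, and the count in SAP 15.1.1 could be its numerator. The 2-night intent is stated in several places. The output templates that accompany the SAP, which are not among the documents reviewed, might show the scale.

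Much of this stands as evidence of intent, and the wording is partly ambiguous. It does not supply the missing step. SAP 15.1.1 defines a count, SAP 15.1.2 repeats it, and the word average fits a group mean of counts equally well. A prespecified equivalence rule should not have two defensible readings with opposite results.

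Three limits are accepted. Equal rates near zero would also satisfy the literal rule, although that is implausible in this population. The equal-rate and correlation scenarios are assumptions. And with matched scales the t interval at 15/30 gives 91% to 97%, short of the stated 99%; that is a separate matter from the scale error.

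**Conclusion.** The concern holds. As written, the only success criterion mixes scales, and its literal margin is 0.286 nights instead of 2. At the plan's own rates the literal rule has essentially no chance of success at any planned size, whereas the matched rule succeeds in at least 91% of trials at 15/30 and about 100% at 40/80. The figures rest on the binomial model with independent nights in Protocol 5.2. The zero result does not depend on the choice of t interval and cannot be mended by a larger sample, since 1.05 exceeds 0.286. This is a unit error in the rule, not an unknown margin, and it must be corrected before the primary analysis.

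**What to change.** Put outcome and margin on one scale in the Protocol synopsis, 5.1 and 5.4.2, and in SAP 4.1, 8.1, 15.1.1 and 15.1.3. There are two equivalent ways:
- define each child's outcome as the proportion of wet nights in the last week (count/7) and keep δ = 2/7; or
- keep the count and state δ = 2.0 wet nights per week.

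Remove the wording that attaches 2/7 to wet nights as a unit, and make the imputed outcome in SAP 15.1.2 match the chosen scale. The cost is wording in the two documents. No new data are needed and the intended margin stays as it is. The sample-size calculation already uses the proportion scale, so this correction does not alter its basis.

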15.1.4 Sensitivity Analysis of Primary Variable

The sensitivity analysis will be performed as described in Section 15.1.2 in case of observing 20% or more of the missing date for the primary variable. Descriptive statistics for the analysis population will be computed comparing the original values to the imputed values.

15.2 Secondary Analysis

Analysis of secondary endpoints will include, QoL and sleep quality assessed via a set of validated questionnaires for the participants and their parent/carers at each study clinic visit. In particular:

- Paediatric Incontinence Questionnaire
- World Health Organization Quality of Life
- Paediatric Daytime Sleepiness Scale
- Checklist Individual Strength

Additionally, the perception of DryNites® attributes, compared to previously used absorbent products will be evaluated through 2 specific questionnaires designed for this study.

Secondary analysis will be performed on RND set.

15.2.1 Secondary Variables & Derivations

15.2.1.1 PinQ

Effective Date: 15Jun2018

The PinQ (Bower et al. 2006) measures the emotional impact that urinary incontinence has on a child. It consists of 20 urinary incontinence QoL related questions which are graded on a scale of 0–4 (0=No, 1=Hardly ever, 2=Sometimes, 3=Often, 4=All the time) with a total possible score of 80.

Document:	Y:\Kimberly-Clark\DryNites\Documentation\SAP\DryNites_SAP_v1.0_20200203		
Author:	[name]	Version Number:	1.0
		Version Date:	03Feb2020
Template No.:	RWI_TP_BIOS0013 Revision 1		Reference: RWI_WI_BIOS0015

Two factors scores cast the items from the children's questionnaires into 2 groups, which could be considered as extrinsic (items 2, 3, 6, 12, 16 and 20) and intrinsic (items 1, 4, 5, 7, 8, 9, 10, 11, 13, 14, 15, 17, 18, 19, 20) impact. Intrinsic items generally related to how the child felt or what they believed, whilst the extrinsic items were more likely to relate to external limitations imposed by urinary symptoms.

The factor score will be obtained as the sum of items included in each factor and the total score will be calculated as the sum of each single non-missing score. Scores will indicate the impact urinary incontinence has on the child's QoL with the higher score indicating a more significant effect.

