# 4.5.2.1. Paediatric Incontinence Questionnaire (PinQ)

The PinQ will be used to assess the child's QoL. The PinQ is a validated cross-cultural continence-specific paediatric QoL questionnaire to assess children with bladder dysfunction, developed by Bower et al. (Bower et al. 2006). It is available as self-rated and proxy versions. This will be completed by the child themselves in the older participant group and will be completed by the parent/carer on behalf of the child in the younger participant group.

The PinQ measures the emotional impact that urinary incontinence has on a child. It consists of 20 urinary incontinence QoL related questions divided in 2 dimensions: intrinsic (14 items) and extrinsic (6 items), which are graded on a scale of 0 to 4 (0=No, 1=Hardly ever, 2=Sometimes, 3=Often, 4=All the time) with a total possible global score of 80.

The total score indicates the impact urinary incontinence has on the child's QoL with the higher scores indicating a more significant effect.

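### SAP 15.2.1.1 lists PinQ item 20 in both factors, so the intrinsic score has 15 items against the protocol's 14; the PinQ total score is unaffected

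*SAP*

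**What the plan says.** Protocol 4.5.2.1 describes 20 questions, each scored 0 to 4, "divided in 2 dimensions: intrinsic (14 items) and extrinsic (6 items"), "with a total possible global score of 80". It gives the number of items in each dimension but not the item numbers.

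SAP 15.2.1.1 repeats the overall structure: "It consists of 20 urinary incontinence QoL related questions which are graded on a scale of 0–4", "with a total possible score of 80". It then names the items in each factor:

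- "extrinsic (items 2, 3, 6, 12, 16 and 20")
- "intrinsic (items 1, 4, 5, 7, 8, 9, 10, 11, 13, 14, 15, 17, 18, 19, 20) impact"

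The scoring rule is "The factor score will be obtained as the sum of items included in each factor". The total is derived separately, by adding the single non-missing item scores. SAP 15.2.2 adds two rules that cover the PinQ domain scores. A score needs at least 50%+1 of its questions answered. A subscale with gaps is prorated: its sum is multiplied by the number of items in the subscale and divided by the number answered. Results with and without this substitution are to be shown.

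**The concern.** The SAP presents the factors as a division of the 20 items into two groups, yet item 20 belongs to both. Because each factor score is the sum of its listed items, the list is in effect the programming specification. The item count also enters the prorating and the completion rule.

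The output at stake is the intrinsic domain score. Protocol 5.4.2 and SAP 15.2.3.1 plan summaries of domain scores and their changes from baseline on the Randomised Set, and the intrinsic score would carry the error into those tables. A group difference on item 20 would also appear in both factors, which blurs the distinction that the two scores are meant to describe.

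**Working it through.** **Inputs.** Item counts and maximum: protocol 4.5.2.1. Item lists, factor rule and total rule: SAP 15.2.1.1. Prorating and completion rule: SAP 15.2.2. Every item is scored 0 to 4, so a factor's maximum is 4 × its number of items.

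**Protocol figures.** 14 + 6 = 20 items and 20 × 4 = 80. These agree with each other and with the 20 items and maximum of 80 stated in the SAP.

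**SAP lists as written.**

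- Extrinsic: 2, 3, 6, 12, 16, 20, which is 6 items; maximum 6 × 4 = 24.
- Intrinsic: 1, 4, 5, 7, 8, 9, 10, 11, 13, 14, 15, 17, 18, 19, 20, which is 15 items; maximum 15 × 4 = 60.
- Entries: 6 + 15 = 21. Distinct items: 20. No item from 1 to 20 is missing, and the only overlap is item 20.
- Factor maxima: 24 + 60 = 84, against a total of 80.

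**Possible repairs.**

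- Item 20 in extrinsic only: 6 + 14 = 20 items, maxima 24 + 56 = 80. This matches the protocol.
- Item 20 in intrinsic only: 5 + 15 = 20 items, maxima 20 + 60 = 80. This does not match the protocol's 14/6.

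**Effect on one child's intrinsic score.** Let S be the sum over the n answered items among the other 14, and x the item 20 response.

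- Complete data (n = 14): SAP list S + x; 14-item list S. The difference is x, from 0 to 4 points.
- Item 20 and n others answered: SAP list (S + x) × 15/(n + 1); 14-item list S × 14/n.
  - n = 8, S = 0, x = 4: 4 × 15/9 = 6.7 against 0. The error exceeds 4 points.
  - n = 8, S = 32, x = 0: 32 × 15/9 = 53.3 against 32 × 14/8 = 56. The error is negative.

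**Effect on who gets a score.** The 50%+1 rule gives 0.5 × 15 + 1 = 8.5 with 15 items, so 9 answers are needed; with 14 items it gives 0.5 × 14 + 1 = 8. A child with 8 of the 14 items answered and item 20 blank has a score under the 14-item list and none under the SAP list.

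**Total score.** It is summed from single items and not from the two factors, so item 20 enters once and the range stays 0 to 80.

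**The case against.** The count cannot be disputed, but there is a fair case that little depends on it.

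- **No named endpoint is affected.** Protocol Table 1 names the change in total PinQ score. This stands. A reader might infer from the double listing that item 20 is counted twice in the total; the SAP's total rule excludes that.
- **The inferential weight is low.** SAP 8.1 plans no confirmatory testing, SAP 15.2.3.1 treats the ANCOVA p-values as exploratory, and neither document says that the intrinsic factor will be modelled. This stands. The descriptive summaries of domain scores are still affected.
- **Not every child is mis-scored.** A reader might infer that all children are. A child with complete data who scores 0 on item 20 gets the same intrinsic score either way. The same list also applies to both arms and all visits, so no between-group bias is shown.
- **The effect size may move little.** SAP 7.4 divides change by baseline SD, and an extra item alters both. The documents do not allow the size or direction to be computed.
- **The repair is not proven.** A reader might infer that item 20 must be extrinsic. The protocol gives counts only, so 14/6 would also result if item 20 were intrinsic and another listed intrinsic item belonged in extrinsic. SAP section 2 also cites plan version 1.0, while the 14/6 text reviewed here is in version 3.0. Confirmation is therefore needed, although the SAP's lists conflict with its own 20 items and 80 points whatever the protocol says.

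Nothing suggests that the overlap is intended. SAP 4.3 declares no change to PinQ scoring, and the SAP's other multi-domain instruments divide cleanly: CIS 8 + 5 + 4 + 3 = 20, and WHOQoL-BREF 7 + 6 + 3 + 8 = 24 plus 2 separate items = 26.

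**Conclusion.** The point holds as an error in the specification of one secondary domain score. As written, the intrinsic score runs to 60 instead of 56, which is 4/56 or 7% on the theoretical maximum and not an estimate of the shift in observed scores. The 0-to-4-point inflation applies to complete data only; with prorating, the error can be larger or can reverse sign. The primary endpoint and the PinQ total score are untouched.

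These sizes assume that item 20 belongs to the extrinsic factor alone, which is the simplest reading that agrees with the protocol. The questionnaire's scoring source is not among the documents, so its allocation remains to be confirmed.

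**What to change.** Reconcile SAP 15.2.1.1 with protocol 4.5.2.1 in this order:

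1. Check item 20's factor against the questionnaire's scoring source.
2. If it is extrinsic, delete it from the intrinsic list. This is the only single edit that gives 14 and 6 items with each item used once. If the source says otherwise, correct both lists from it.
3. Use 14 as the intrinsic item count in the SAP 15.2.2 prorating and completion threshold (8 answers).

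The cost is one look-up and a one-line SAP edit before the scores are programmed. No data collection changes. Left alone, the programmer must either follow a list that contradicts the instrument's stated size or correct it without a record.

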#### 5.4.5. Handling of Missing Data

Should missing data occur, the data will be analysed as recorded in the study eCRFs, that is, analyses will be performed on patients with non-missing values. However, the number of missing values for data elements will be reported, and the likely impact of missing data on the analysis and the pattern of the missing information will be assessed.

Depending upon the amount of missing data, and whether there is evidence of bias in the missing data (e.g., differences between patients with and without missing data), an imputation strategy, such as multiple imputation, may be performed. If an imputation strategy is undertaken, a sensitivity analysis will be carried out comparing the results from the complete case analysis (where records with missing data will be dropped) and the full set analysis including the imputed data. Full details on handling of missing data will be described in detail in the SAP.

Handling of missing item responses in QoL and sleep questionnaires will be performed according to their respective scoring manuals.

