15.2.2 Missing Data Methods for Secondary Variables

No reliable methods are proposed to manage missing data in PinQ, PDSS and CIS. Please see Section 15.2.1.2 for instruction on missing management for WHOQoL-BREF.

Total scores and the domain scores (applicable for PinQ and CIS only) will be calculated in case of at least 50%+1 of questions completed and the subscale score will be prorated by multiplying the sum of the subscale by the number of items in the subscale, then dividing by the number of items actually answered. The results obtained will be presented along with results obtained without missing substitution.

No missing substitutions will be applicable on Absorbent Pants and DryNites® Clinical Trial Questionnaires.

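### The PinQ total is defined as a sum of answered items, which scores every skipped item as 0, and the SAP does not say whether a prorated total replaces it in the analysis

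*SAP*

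**What the plan says.** SAP 15.2.1.1 describes the PinQ: "It consists of 20 urinary incontinence QoL related questions". The coding is "0=No, 1=Hardly ever, 2=Sometimes, 3=Often, 4=All the time", "with a total possible score of 80", and scores are read "with the higher score indicating a more significant effect", so a high total is a bad one. The derivation then states that "the total score will be calculated as the sum of each single non-missing score". The same section lists the items of the extrinsic and intrinsic factors, and item 20 appears in both lists.

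SAP 15.2.2 deals with missing items. It says that no dependable method exists for the PinQ, PDSS and CIS, and then gives one. Total and domain scores "will be calculated in case of at least 50%+1 of questions completed", and the subscale score is scaled up from the answered items to the full number of items. On reporting it adds: "The results obtained will be presented along with results obtained without missing substitution".

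SAP 15.2.3.1 plans summaries, changes from baseline and an ANCOVA at Visit 3, without naming the version of the score to be used. Protocol Table 1 makes the change from baseline in the PinQ total at Day 56 the child quality-of-life endpoint. Protocol 5.4.5 has a different rule for blanks: "Handling of missing item responses in QoL and sleep questionnaires will be performed according to their respective scoring manuals".

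**The concern.** A sum over answered items is the same number as a sum over all items with each blank set to 0. On this scale 0 is the most favourable answer, so a partly completed form shows less impact than the child has. For the WHOQoL-BREF the SAP avoids this: a missing item takes the mean of the other items in its domain (SAP 15.2.1.2).

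SAP 15.2.2 does not clearly remove the problem. Its threshold covers totals, but its prorating sentence covers only the subscale score. The one explicit formula for the PinQ total is therefore the plain sum. If the prorating is meant to extend to the total, two formulas exist and an analyst has to choose between them.

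At stake is whether the PinQ comparison measures quality of life or, in part, how fully the forms were completed. The trial is open-label and allows questionnaires to be completed remotely.

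**Working it through.** **Inputs from the documents.** 20 items, each scored 0 to 4, higher is worse (SAP 15.2.1.1); 50%+1 completion (SAP 15.2.2); endpoint is change from baseline (Protocol Table 1). **Assumptions.** The documents give no item means and no item-level missing rates, so item means of 1, 2 and 3 are used, with skipped and answered items sharing the same mean unless stated.

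1. *The plan's own figure.* Maximum total = 20 × 4 = 80, as stated.

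2. *Threshold.* 50% of 20 is 10, plus 1 gives 11 items. At most 20 − 11 = 9 items can be blank. The SAP does not say whether the threshold also applies to the unsubstituted version; if it does not, more could be blank.

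3. *Plain sum on one form.* With k items skipped and item mean m, the sum is m × (20 − k). The loss is k × m points, or k/20 of the complete total.

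| Item mean | Complete | 1 skipped | 2 skipped | 4 skipped | 9 skipped |
|---|---|---|---|---|---|
| 1 | 20 | 19 | 18 | 16 | 11 |
| 2 | 40 | 38 | 36 | 32 | 22 |
| 3 | 60 | 57 | 54 | 48 | 33 |
| Loss | – | 5% | 10% | 20% | 45% |

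4. *Prorated total.* Sum × 20 / (20 − k). At item mean 2 with two skipped: 36 × 20/18 = 40; with nine skipped: 22 × 20/11 = 40. This exact recovery follows from the equal-means assumption. If four items rated 4 are skipped and the other sixteen are rated 2, the true total is 16 + 32 = 48, the plain sum is 32, and the prorated total is 32 × 20/16 = 40. Prorating halves that error (from 16 points to 8) but does not remove it.

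5. *Change from baseline, no true change, item mean 2.* Two items blank at Visit 3 only: 36 − 40 = −4, a false improvement. Two items blank at baseline only: 40 − 36 = +4, a false worsening.

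6. *Difference between arms.* Let f be the difference between arms in the share of incomplete Visit 3 forms. With the same k and m in both arms and no baseline imbalance, the bias is f × k × m. At m = 2:
   - f = 0.05, k = 1: 0.05 × 1 × 2 = 0.1 points
   - f = 0.10, k = 2: 0.10 × 2 × 2 = 0.4 points
   - f = 0.20, k = 4: 0.20 × 4 × 2 = 1.6 points

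   The arm with more incomplete forms at Visit 3 looks better. With f = 0 the bias is 0.

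7. *Factor lists.* SAP 15.2.1.1 lists 6 extrinsic and 15 intrinsic entries, 21 in all, because item 20 is counted twice. A total built by adding the factors could reach 21 × 4 = 84. Protocol 4.5.2.1 gives 14 + 6 = 20 items.

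**The case against.** The best defence is that SAP 15.2.2 is the section on missing items. It sets a completion threshold, prorates, and openly plans a second set of results without substitution. On that reading the plain sum is simply the second set. This stands against any claim that the SAP contradicts itself, which a reader might infer from the two sections. It does not settle which set is analysed, or whether the total is prorated at all.

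Two further points stand. The endpoint is a change, so blanks do not always favour better quality of life, and equal missingness in both arms cancels in the group comparison. Also, SAP 8.1 plans no confirmatory testing and SAP 15.2.3.1 labels these p-values exploratory. Nothing here reaches the primary equivalence conclusion.

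A reader might also carry the point over to the CIS, where items start at 1, and argue that blanks push scores off the scale or below the severe-fatigue cut-off of 35. The documents do not support this. SAP 15.2.1.4 defines each CIS domain as a sum of its items with no rule about summing only the answered ones. The cut-off appears in Protocol 4.5.2.4 as background, and no planned analysis classifies parents by it.

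**Conclusion.** The point holds in limited form. The stated formula for the PinQ total is wrong for incomplete forms, and the missing-data section does not clearly replace it. Each skipped item costs 1 to 3 points for assumed item means of 1 to 3, up to 45% of the total if nine items are blank. That worst case is a bound, not a forecast.

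The likely effect on the comparison between arms is much smaller: about 0.1 to 1.6 points on an 80-point scale, and only if completeness differs by arm. The imbalances behind that range are assumptions. Within-group changes, which SAP 15.2.3.1 also reports, can be distorted even with balanced arms if completeness differs between baseline and Visit 3. The correction is worth making because it costs almost nothing and removes a choice between two versions of a named endpoint.

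**What to change.** - **SAP 15.2.1.1:** replace the plain sum with total = sum of answered items × 20 / number answered if at least 11 items are answered, otherwise missing. Name this as the version used for the change from baseline and the ANCOVA.
- **Prorate over the 20 items directly**, not by adding prorated factors, and reconcile the double listing of item 20 with Protocol 4.5.2.1.
- **SAP 15.2.2:** define the unsubstituted results as complete forms only, so that no blank is scored 0.
- **Protocol 5.4.5:** check the rule against the scoring manual to which it defers, and record any departure in SAP 4.3, which at present lists none on this point. The SAP was written against version 1.0 of the clinical investigation plan, so this check is also part of bringing it up to date.

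The cost is a few sentences and no new data. The complete-forms table will cover fewer forms, and prorating leaves some bias where skipped items differ from answered ones.
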